## **6.3 MEASURES TO MINIMIZE BIAS: RANDOMIZATION AND BLINDING**

This is an open-label and non-randomized study; participants who meet all the inclusion criteria and none of the exclusion criteria will be eligible for inclusion in the study. Each participant will be registered and receive an incremental identification number per site corresponding to his/her order of enrollment in the study.

## 6.4 STUDY INTERVENTION COMPLIANCE

### 6.4.1 Treatment accountability and compliance

Administration of the study treatment will be supervised by the Investigator or Sub-investigator.

The person responsible for drug dispensing is required to maintain adequate records of the IMP. These records (eg, drug movement form) include the date the IMP is received from the Sponsor, dispensed for patient and destroyed or returned to the Sponsor. The packaging batch number (IP00xxxx) must be recorded on the drug accountability form.

The person responsible for drug administration to the patient will record precisely the date and the time of the drug administration to the patient.

### 6.4.2 Return and/or destruction of treatments

Partially used and used IMP will be destroyed at the study site according to the standard practices of the site after an accurate accountability has been performed and signed by the Investigator (or the Pharmacist). A detailed treatment log form of the destroyed IMP will be established with the Investigator (or the Pharmacist) and countersigned by the Investigator and the Monitoring Team.

The Investigator must not destroy the unused IMP unless Sanofi provides written authorization. Further guidance and information for the accountability purpose of use and unused study interventions are provided in the pharmacy manual.

## 6.5 CONCOMITANT THERAPY

Any medication that the participant is receiving at the time of enrollment or receives during the study must be recorded along with:

- Reason for use
- Dates of administration including start and end dates
- Dosage information including dose and frequency

The Medical Monitor should be contacted if there are any questions regarding concomitant or prior therapy.

Participants who experience an infusion reaction may be treated post-injection with the medications listed in [Section 6.1](#), as well as additional medications, if deemed necessary by the investigator.

The SARS-CoV-2 vaccine is permitted during the study, as per local standard of care, investigator discretion, and local labels. If feasible, it is preferable that the last dose of the SARS-CoV-2 vaccine be administered at least 2 weeks prior to the first dose of isatuximab, or for the vaccine to be administered 30 days or more after the final dose of isatuximab.

HBV vaccination could be considered, following investigator's discretion, for participants with negative HBsAg, total anti-HBc, anti-HBs and HBV-DNA. At least 3 doses of vaccine will be administered at monthly intervals, the first one 1-2 weeks before start of study treatment. Anti-HBs should be monitored at 1, 2, and 3 months after the end of vaccination. Anti-HBs above 100 mU/mL indicates good seroconversion, between 10 and 100 mU/mL moderate seroconversion that can be limited in time, and less than 10 mU/mL indicates no response to vaccination.

If antiviral therapy for HBV or HCV was started before initiation of IMP and the patient was eligible for the trial, the antiviral therapy for HBV or HCV should continue throughout the treatment period as recommended by a specialist.

In case of viral reactivation during study treatment (greater than  $1\log_{10}$  IU/mL increase in HBV DNA or reappearance of HBsAg or detection of HBV DNA in participants with resolved infection\*), study treatment will be held and a specialist consulted for initiation of anti-viral treatment and monitoring of the patient. Restart of study treatment should be agreed between sponsor, investigator and specialist (hepatologist) if infection is controlled. Close monitoring of ALT and AST should continue up to study treatment discontinuation. HBV DNA to be monitored as per specialist advice.

*\*Previous known history of acute or chronic hepatitis B or the presence of total anti-HBc with/without anti-HBs; HBsAg negative; undetectable serum HBV DNA; normal ALT levels.*

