### Medical conditions

- Clinically significant medical history or ongoing chronic illness that would jeopardize the safety of the participant or compromise the quality of the data derived from his or her participation in the study as determined by the Investigator.
- Serious infection that required hospitalization within 3 months prior to enrollment.
- Secondary wAIHA from any cause including drugs, lymphoproliferative disorders, infectious or autoimmune disease (SLE without other SLE-related manifestations apart from cutaneous and musculoskeletal manifestations is allowed), or active hematologic malignancies. Participants with positive antinuclear antibodies but without a definitive diagnosis of an autoimmune disease are allowed.
- History of coagulation or bleeding disorders (Evans Syndrome is allowed).

E 05. Uncontrolled or active HBV infection: Participants with positive HBsAg and/or HBV DNA. Of note:

- Patient can be eligible if anti-HBc IgG positive (with or without positive anti-HBs) and HBsAg and HBV DNA are negative.
  - If anti-HBV therapy in relation with prior infection was started before initiation of IMP, the anti-HBV therapy and monitoring should continue throughout the study treatment period.
- Participants with negative HBsAg and positive HBV DNA observed during screening period will be evaluated by a specialist for start of anti-viral treatment; study treatment could be proposed if HBV DNA becomes negative and all the other study criteria are still met.

Active HCV infection: positive HCV RNA and positive anti-HCV. Of note:

- Participants with antiviral therapy for HCV started before initiation of IMP and positive HCV antibodies are eligible. The antiviral therapy for HCV should continue throughout the treatment period until seroconversion.
- Participants with positive anti-HCV and undetectable HCV RNA without antiviral therapy for HCV are eligible.

E 06. HIV infection.

E 07. Positive SARS-CoV-2 molecular test (if COVID-19 testing required).

E 08. Serum gammaglobulin levels <3 g/L.

E 09. Ferritin levels below the lower limit of normal.

E 10. Alanine aminotransferase (ALT) and aspartate aminotransferase (AST) >3 x ULN.

E 11. Prothrombin time (PT/INR) or activated partial thromboplastin time (aPTT) above the ULN and deemed to be clinically significant by the Investigator.

E 12. WBC count < 3.0 x 10^9/L or neutrophil count < 1.5 x 10^9/L

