**Table 10 - Protocol-required laboratory assessments**

Laboratory assessments	Parameters
Hematology (local lab)	Platelet count Red blood cell (RBC) count Hemoglobin Hematocrit RBC indices: MCV MCH Reticulocytes White blood cell (WBC) count with differential: Neutrophils Lymphocytes Monocytes Eosinophils Basophils Markers of hemolysis: LDH Haptoglobin Total bilirubin Direct Antiglobulin Test
Clinical chemistry	Blood urea nitrogen (BUN) Creatinine Glucose (non-fasting) Potassium Sodium Calcium Aspartate aminotransferase (AST)/Serum glutamic-oxaloacetic transaminase (SGOT) Alanine aminotransferase (ALT)/Serum glutamic-pyruvic transaminase (SGPT) Alkaline phosphatase Total and direct bilirubin Total protein
Coagulation	PT/INR PTT
Other tests	Ferritin (Screening only) FSH (screening only, when applicable) Serology (screening only): HIV antibody, hepatitis B surface antigen (HBsAg), anti-HBs, anti-HBc (total and IgM, followed by HBV DNA in case of anti-HBc positivity), and hepatitis C virus antibody, hepatitis C virus RNA (if positive anti-HCV Ab) SARS-CoV-2 molecular test

Laboratory assessments	Parameters
	Quantitative immunoglobulins (IgA, IgG, IgM) Measles, mumps, tetanus, diphtheria titers
Routine urinalysis	

• Specific gravity

• pH, glucose, protein, blood, ketones, bilirubin, urobilinogen, nitrite, leukocyte esterase by dipstick

• Microscopic examination (if blood or protein is abnormal)

Investigators must document their review of each laboratory safety report.

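### Section 6.5 holds dosing on HBsAg or HBV DNA results in resolved hepatitis B, but no readable text dates either test after screening for participants not on anti-HBV therapy

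*Protocol*

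**What the plan says.** **The stop rule.** Protocol Section 6.5 opens it with "In case of viral reactivation during study treatment". The listed signs are a rise in HBV DNA of more than 1 log10 IU/mL and "reappearance of HBsAg or detection of HBV DNA in participants with resolved infection". Dosing is then held, a specialist is consulted, and restart needs agreement between sponsor, investigator and hepatologist.

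**Who it covers.** The footnote to Section 6.5 defines resolved infection as a known history of hepatitis B or "the presence of total anti-HBc with/without anti-HBs; HBsAg negative; undetectable serum HBV DNA; normal ALT levels". Section 5.2, criterion E 05, lets these people in: "Patient can be eligible if anti-HBc IgG positive (with or without positive anti-HBs) and HBsAg and HBV DNA are negative". Anti-HBV therapy is not a condition of entry. Where it was started before isatuximab, "the anti-HBV therapy and monitoring should continue throughout the study treatment period".

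**When the tests are done.** Table 10 (Section 10.2) reads "Serology (screening only): HIV antibody, hepatitis B surface antigen (HBsAg), anti-HBs, anti-HBc (total and IgM, followed by HBV DNA", the HBV DNA test being a reflex after a positive anti-HBc. SoA footnote f lists the same tests and dates only one later measurement, anti-HBs at 1, 2 and 3 months after HBV vaccination. Section 6.5 considers vaccination only in participants negative on all HBV markers.

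**Other monitoring.** Section 6.5 adds "Close monitoring of ALT and AST should continue up to study treatment discontinuation" and "HBV DNA to be monitored as per specialist advice". ALT above 3 x ULN is an adverse event of special interest (Section 8.3.6). Section 7.1.1 asks the investigator to consider stopping treatment for abnormal liver function under Section 10.6. Section 10.2 lets the investigator order additional tests at any time.

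**The concern.** The hold depends on laboratory results, so it can act only if someone orders the test. For participants with resolved infection who are not on anti-HBV therapy, the text names the results that stop dosing and confines those tests to screening. Detection then depends on a rise in ALT or on a test ordered at discretion. Both can come after the virus has become detectable, and dosing could continue in the meantime.

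The rule also speaks only of reactivation during treatment. Follow-up after the last dose of a six-dose course is 169 - 71 = 98 days, or 14 weeks, and Section 6.5 orders no specialist referral for reactivation found in that period. Section 8.3.3 follows serious events and events of special interest to resolution or stabilization, but that does not order a referral.

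Participant safety is at stake. The sample size and the efficacy analysis are not affected.

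**Working it through.** **1. Text check.** The plan gives no figure to reproduce. I looked for any HBsAg or HBV DNA test dated after screening for a participant with resolved infection and no anti-HBV therapy.

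| Place | Finding |
|---|---|
| Table 10 | Both tests at screening only |
| SoA hepatitis row | No readable visit mark at all, so it says nothing either way |
| SoA footnote f | Dates only anti-HBs after vaccination, in a different group |
| E 05 | Continued monitoring only with anti-HBV therapy started before isatuximab |
| Section 6.5, specialist sentence | No date or interval; follows the text on hold, consultation and restart |
| Sections 7.1.1, 8.3.6, 10.6 | Act on liver abnormality; Appendix 6 flowchart not shown |
| Section 10.2, additional tests | Permitted, not required |

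Dated later tests in the readable text: 0.

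**2. Worst-case doses after detectability.** Inputs are dosing on Days 1, 15, 29, 43, 57 and 71, and the SoA windows matched in order to the visits: Days 15 and 29 ±1 day; Days 43, 57 and 71 ±2 days. Turnaround T of the assay is an assumption. A sample at visit v stops the next dose d if its result arrives before the dosing day, with the sample as late and the dose as early as the windows allow:

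(v + window) + T < d - window

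- Day 29 sample, Day 43 dose: 30 + T < 41, so T must be 10 days or less.
- Day 57 sample, Day 71 dose: 59 + T < 69, so T must be 9 days or less.

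| First detectable after dosing on | No scheduled test | Tests Days 29 and 57, T up to 9 d | Same tests, T = 14 d |
|---|---|---|---|
| Day 1 | 5 | 2 (Days 15, 29) | 3 (Days 15, 29, 43) |
| Day 15 | 4 | 1 (Day 29) | 2 (Days 29, 43) |
| Day 29 | 3 | 2 (Days 43, 57) | 3 (Days 43, 57, 71) |
| Day 43 | 2 | 1 (Day 57) | 2 (Days 57, 71) |
| Day 57 | 1 | 1 (Day 71) | 1 (Day 71) |
| **Maximum** | **5** | **2** | **3** |

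At T = 10 days the Day 57 result can arrive on Day 69 (59 + 10), too late for the earliest Day 71 dose, so the maximum is already 3. Testing at every dosing visit from Day 15 gives a maximum of 1 for T up to 9 days and 2 for 10 to 14 days.

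**3. First Cohort 1 course.** It has only two doses (Days 1 and 15), so a Day 29 test prevents none. It would inform retreatment, which starts only after the Day 43 visit (Section 4.1).

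**The case against.** The strongest reply is that the absence is not proven. Section 8.2.4 sends timing and frequency to the SoA and requires conduct according to the laboratory manual and the SoA. The hepatitis row of the SoA lost its visit marks, the manual is not among the documents, and the Appendix 6 flowchart may include HBV tests once ALT has risen. The Table 10 label is not exhaustive either, since anti-HBs sits under the same heading and is repeated after vaccination. All of this stands as a limit. But the vaccination exception is written out and concerns other participants. If the SoA did schedule a later test, Table 10 would contradict it and would still need correcting.

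A second reply is that the specialist sentence delegates the interval to a hepatologist. It could be read that widely. However, it follows the reactivation text and sets no interval, and no readable text sends an untreated participant with resolved infection to a specialist beforehand.

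Third, the liver is watched. ALT and AST are in the chemistry panel, whose SoA row carries marks beyond screening. That stands: what lacks a date is the virological test. ALT remains an indirect signal and is not a hold trigger.

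Fourth, the dose counts are extremes. They assume the least favorable onset and no intervening ALT signal or discretionary test, and no rate in the documents says how often this would happen. That also stands.

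A reader might further infer that retreated Cohort 1 participants certainly face the same gap. The documents do not settle this. SoA footnote e applies the SoA safety assessments to retreatment, and the hepatitis row sits under that heading, so the tests may be repeated. Whether that includes the screening column is unclear.

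**Conclusion.** The point holds on the readable text and rests on the Table 10 label. A stated virological hold has no dated test behind it for participants with resolved hepatitis B who are not on anti-HBV therapy. Participants on such therapy started before isatuximab are outside the finding. The worst case is 5 further doses in a six-dose course. Tests on Days 29 and 57 would cut this to 2 with results within 9 days, or 3 with results in 10 to 14 days.

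A reader might infer that the plan schedules no hepatitis B testing after screening for anyone, or that a participant was dosed through a reactivation. The documents support neither. The SoA row cannot be read, and no document shows that an enrolled participant was in this subgroup.

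The practical effect in this study is small. Part A has at most 9 participants (Section 9.2.1), the study stopped early, and Part B was not performed (SAP Section 1.2). One Cohort 1 participant was retreated (SAP Section 1.3), with no HBV status given. This is a cheap safety improvement with no bearing on the efficacy results. Confidence is medium because of the unreadable and unavailable sources.

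**What to change.** **Testing.** In Table 10 and the SoA, for participants who meet the Section 6.5 footnote definition (known hepatitis B history or positive total anti-HBc, with its other conditions) and are not already monitored under anti-HBV therapy, add HBV DNA and HBsAg at existing visits about every 4 weeks, for example Days 29, 57, 85, 113, 141 and 169. A specialist may set a shorter interval. State explicitly that the same schedule runs from the first retreatment dose in Cohort 1. The 4-week interval is a proposal. It fits the visit grid and matches the pregnancy testing in Table 1 of the protocol, but is not derived from HBV kinetics.

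**Referral.** In Section 6.5, extend the specialist referral to reactivation found during follow-up. The hold and restart decisions stay as written.

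**Cost.** 2 tests x 6 visits = 12 assays per affected participant per course. The Part A ceiling is (9 + 3) x 12 = 144 assays, if all 9 participants qualified and all 3 in Cohort 1 were retreated; the real number would be far smaller. No new visits are needed. In the first course, PK samples P00 to P12 match the 13 visits from Day 1 to Day 169. In retreatment, blood counts and hemolysis markers are already drawn per the SoA. The wording changes, including the laboratory manual, need an amendment with IRB/IEC approval (Section 10.1.1).

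### The rule in Protocol 6.5 that any detected HBV DNA stops dosing covers only participants with normal ALT, although E 05 and E 10 allow anti-HBc-positive participants with raised ALT to enter

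*Protocol*

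**What the plan says.** Protocol 6.5 (Concomitant therapy) defines viral reactivation by three alternatives. The first is a rise of more than 1 log10; the full list ends "IU/mL increase in HBV DNA or reappearance of HBsAg or detection of HBV DNA in participants with resolved infection". On any of them, "study treatment will be held and a specialist consulted for initiation of anti-viral treatment and monitoring of the patient".

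An asterisk on the third alternative leads to a footnote. Resolved infection means a known history of hepatitis B or "the presence of total anti-HBc with/without anti-HBs; HBsAg negative; undetectable serum HBV DNA; normal ALT levels".

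Entry is governed by Protocol 5.2:

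- E 05 excludes "Uncontrolled or active HBV infection: Participants with positive HBsAg and/or HBV DNA".
- E 05 then allows: "Patient can be eligible if anti-HBc IgG positive (with or without positive anti-HBs) and HBsAg and HBV DNA are negative". No ALT condition is attached.
- E 10 excludes "Alanine aminotransferase (ALT) and aspartate aminotransferase (AST) >3 x ULN".

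On testing after entry, Protocol Table 10 and footnote f of the schedule of activities place HBV serology, with HBV DNA if anti-HBc is positive, at screening. E 05 asks that anti-HBV therapy begun before study drug for a prior infection, and the monitoring that goes with it, carry on through the treatment period. Section 6.5 closes its reactivation paragraph with "HBV DNA to be monitored as per specialist advice".

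**The concern.** The population let in and the population covered by the most sensitive hold rule do not match. Two anti-HBc-positive participants could enter with the same negative HBsAg and HBV DNA, and later show the same low level of HBV DNA. The one who entered with normal ALT must have dosing held and a specialist consulted. For the one who entered with raised ALT, the protocol leaves the hold to judgment until another trigger is met.

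The difference runs against caution, because the weaker rule applies to the participant whose liver tests were already abnormal. It also departs from the protocol's own entry rule, under which positive HBV DNA is disqualifying whatever the ALT. The protocol gives no reason for the difference, and section 2.3.2 raises the possibility that isatuximab lowers antiviral antibodies. What is at stake is participant safety in a rare situation, not the estimate of any endpoint.

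**Working it through.** The plan gives no figure to reproduce here. The check compares who may enter with who is covered, and then applies each trigger to the difference.

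**Step 1: who may enter.** Under E 05 and E 10 together: anti-HBc positive, HBsAg negative, HBV DNA negative, ALT up to about 3 x ULN. The upper edge is inexact, because E 10 joins the two enzymes with 'and' and could be read as needing both above the limit. The gap does not depend on that edge. Appendix 6 (section 10.6) has a rule for a baseline ALT above ULN, so raised baseline values are foreseen.

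**Step 2: who the footnote covers.** The same serology and DNA status, with ALT at or below 1 x ULN. The footnote gives no time for the ALT condition. It is read here at entry, because undetectable HBV DNA stands in the same list and can only describe the state before detection.

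**Step 3: the difference.** Eligible but not covered: entrants with ALT above ULN.

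**Step 4: apply the triggers to newly detected low-level HBV DNA, HBsAg still negative.**

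| Rule in 6.5 | Entry ALT normal | Entry ALT above ULN |
|---|---|---|
| Rise above 1 log10 | depends on how the rise is counted | depends on how the rise is counted |
| HBsAg reappears | not met | not met |
| Any detection, resolved infection | met: hold required | not met: footnote fails on ALT |

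One trigger of three is affected. Larger DNA rises and HBsAg reappearance still compel a hold in both columns.

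**Step 5: can the gap be sized?** A rise above 1 log10 means log10(new / baseline) > 1, that is, new > 10 x baseline. The baseline here is an undetectable result with no numeric value. Section 6.5 gives neither an assay limit nor a convention for it, so no upper end can be calculated.

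**Step 6: do other rules close the gap?** Section 7.1.1 asks the investigator to consider stopping for abnormal liver function, and 7.1.2 allows a temporary stop for suspected adverse events. The event of special interest in 8.3.6 is ALT above 3 x ULN. The first two are discretionary, and the third responds to ALT. None mandates a hold on an HBV DNA result. The Appendix 6 flowchart is not in the text available for this review; its title and notes concern ALT increase.

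**Step 7: reach.** Protocol 9.2.1 caps Part A at 9 participants (3 cohorts x 3), and SAP 1.2 states that Part B was not performed. The documents give no frequency of anti-HBc positivity or raised ALT.

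**The case against.** The strongest reply is that the rule can rarely operate. No HBV DNA test is scheduled after screening for an untreated participant, so the detection trigger works only if someone has chosen to test, and that holds equally for participants with normal ALT. This largely stands, and it is the main reason the point is minor. It does not make the correction empty: E 05 requires monitoring to continue in those already on anti-HBV therapy, and ad hoc testing is possible.

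A second reply is that some of these participants are already under specialist care. That is true of those on continuing therapy. It is also true of those first found DNA positive at screening, who "will be evaluated by a specialist for start of anti-viral treatment"; they are outside this point. But a specialist's involvement does not itself hold study drug, which is what 6.5 requires.

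Third, eligibility under E 05 is permissive. The first exclusion criterion and E 27 let an investigator decline someone with unexplained raised ALT. They allow this but do not require it.

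Fourth, if undetectable were counted as zero, any detection might be treated as exceeding 1 log10, and there would be no gap. The protocol does not say so. The log10 rise from zero is undefined, and that reading would make the separate detection trigger redundant. It cannot be ruled out, however.

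Two stronger readings are tempting. A reader might infer a definite range of unprotected viral load, for example by borrowing the SAP 1.3 rule that halves values reported as below a limit. That rule was written for descriptive statistics and flags, not for dosing decisions, and does not support a figure. A reader might also infer that these participants have no protection against reactivation. They do: two of the three triggers and investigator judgment remain.

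**Conclusion.** The point holds as a minor correction to the scope of a safety rule. For an eligible anti-HBc-positive participant with raised entry ALT, a newly detected low level of HBV DNA does not by itself require a hold unless it counts as a rise above 1 log10 or HBsAg reappears. No width is claimed for the gap.

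The conclusion rests on three readings: the items after the semicolons in the footnote are all required; ALT is judged at entry; and the resolved-infection qualifier attaches to the detection trigger only. If the second or third reading is wrong, the gap is wider: ALT judged at detection would drop anyone whose ALT had risen by then, and a qualifier that also covered HBsAg reappearance would narrow that trigger as well.

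Few of the at most 9 Part A participants could be concerned, possibly none. No endpoint, population or analysis changes, and nothing in the documents shows that any participant was harmed or handled wrongly. As the study stopped early, the value lies mainly in not carrying the wording into another protocol.

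**What to change.** Delete the ALT item from the footnote to section 6.5. Alternatively, state in 6.5 that the detection trigger applies to every participant with positive anti-HBc or a known history of HBV who was HBsAg negative with undetectable HBV DNA at entry, whatever the entry ALT.

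Either change makes the covered group equal to the admitted group. It also removes the need to settle how a rise from undetectable is counted for these participants, since any detection would then suffice.

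The cost is one line of protocol wording, with no new test, visit or participant. The downside is an occasional extra treatment hold. The change does not add on-study HBV DNA testing, so it improves the response to a result but not the chance of obtaining one.
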